## 2. Background

OAB is a common condition affecting 16.9% of women in the US, with a marked increase in the prevalence of urgency urinary incontinence (UUI) after the age of 44. The International Continence Society (ICS) and International Urogynecologic Association (IUGA) define OAB as a symptom syndrome characterized by urinary urgency, usually accompanied by frequency and nocturia, with or without UUI. The burden of OAB is not only substantial but pervasive. The estimated annual cost of OAB in the US is over \$12 billion. On an individual level, it significantly impairs the quality of life of those who suffer from it, affecting social, psychological, occupational, domestic, physical and sexual aspects of their lives.

PROTOCOL TITLE: INTENSE: INvestigation of TENS Efficacy versus Posterior Tibial Nerve Stimulation for overactive bladder

The 2019 American Urological Association/Society of Urodynamics, Female Pelvic Medicine & Urogenital Reconstruction (AUA/SUFU) Guidelines for the management of OAB includes conservative first and second line treatments with behavior and pharmacologic therapies. However, not all OAB patients respond to or tolerate conservative treatment. The discontinuation rate of anticholinergics is 58.8% at 6 months, worsening to 74.8% at 1 year and 87% at 3 years. Hence, patients often seek alternate therapies. Third line options include PTNS, sacral neuromodulation (SNS) and intradetrusor onabotulinumtoxinA injections, while fourth line therapies are more invasive and morbid surgical treatments such as urinary diversion or augmentation cystoplasty. SNS has a success rate of 54% but requires the implantation of a permanent device, which may deter some patients. Additionally, there are frequent and moderately severe adverse effects associated with SNS, including pain, lead migration, infection/irritation, electric shock and the need for additional surgeries in over 30% of patients. Costs for SNS are substantially higher than other treatments. A cost analysis comparing pharmacologic, SNS, PTNS and onabotulinumtoxinA by Kraus et al. found PTNS had the lowest mean costs at \$6959 over 24 months, while SNS had the highest costs at \$29,702. Intradetrusor onabotulinumtoxinA is another effective treatment with success rates of 60-70%. However it is expensive and associated with adverse effects like urinary tract infections (19.7%) and urinary retention requiring temporary clean intermittent self-catherization (8.4%).

PTNS is a cost effective and less invasive third line treatment option for OAB patients. Multiple studies have examined the efficacy and safety of PTNS for OAB in adults and children. The SUmIT Trial demonstrated PTNS was superior to sham for both objective (voids per day and incontinence episodes) and subjective (improvement in bladder symptoms) parameters of OAB and was shown to have sustained safety and efficacy at 24 months. The OrBIT Study comparing PTNS to extended release tolterodine demonstrated significant improvements in incontinence episodes, voids per day and nocturia in both arms. However, PTNS showed greater subjective improvement over tolterodine for overall health related quality of life (HRQOL) with sustained effects at 12 months. A meta-analysis of PTNS concluded improvement in OAB symptoms is comparable between PTNS and antimuscarinics, but PTNS offers a better adverse event profile. PTNS has mild, transient and rare adverse effects occurring 1-2% and include bruising or bleeding at the needle site, tingling and mild pain with no serious adverse events reported. In comparison, reported adverse events of antimuscarinics range from 9.7-63% and most commonly include constipation, dry mouth, voiding dysfunction, and urinary tract infection (UTI). Current standard treatment protocols involve weekly 30-minute treatments for 12 weeks total. This can pose a significant barrier for patients, requiring multiple clinic visits, time off work, and frequent transportation that can affect compliance and therefore treatment success and patient satisfaction.

A more patient-centered option for OAB with similar success rates may be TENS. TENS is commonly used in physical therapy to treat pain, but recent studies have demonstrated its effectiveness in treating OAB. When compared to controls, patients receiving TENS had significantly greater OAB symptoms improvement (48-93%), UUI cure rates (24-45%) and patient satisfaction. TENS is an incredibly safe and non-invasive therapy with no adverse events reported by any study reporting use of TENS in a systematic review of 10

PROTOCOL TITLE: INTENSE: INvestigation of TENS Efficacy versus Posterior Tibial Nerve Stimulation for overactive bladder

RCTs and 3 prospective cohorts. Women also view TENS as a convenient, beneficial and acceptable treatment of OAB. A qualitative study by Daly et al. revealed TENS home treatment allowed for flexibility to accommodate lifestyle and work needs, unlike clinic visits, and provided a sense of control and empowerment over their OAB symptoms that facilitated their willingness and motivation to continue treatment and improve self esteem^26. The home was viewed as a safe space for women to receive treatment without the stress and embarrassment of clinic visits for their condition. Women in the study often viewed TENS as both a mental and physical treatment. The at home self-administration makes TENS treatment a viable way to reduce obstacles patients face accessing care. This is encouraging evidence that TENS may provide a safe, effective, convenient and possibly preferred alternative treatment to PTNS for OAB.

To date, there are very limited studies directly comparing PTNS and TENS for the treatment of OAB. Ramírez-García et al. compared PTNS to transcutaneous stimulation of the posterior tibial nerve for the treatment of OAB and demonstrated transcutaneous tibial nerve stimulation was non-inferior in decreasing daytime frequency, urinary incontinence episodes and quality of life. However, both interventions in this study were performed in a clinical setting and once a week, overlooking the two significant advantages TENS provides over traditional PTNS: self-administered treatment at home and increased frequency of treatment. Another RCT comparing PTNS to TENS, in which the TENS group received daily treatments at home, did not demonstrate a difference between groups in reductions of incontinence episodes, number of voids or quality of life measures (unpublished data). However, this study was underpowered to determine equivalency or non-inferiority. The authors are unaware of any other trials directly comparing TENS and PTNS treatment for OAB. Given this gap in knowledge and the advantages TENS can offer to reduce barriers to accessing healthcare, we propose to study home TENS versus traditional, office-delivered PTNS for women with OAB. This innovative research shows promise in helping patients overcome a costly and embarrassing condition in the privacy of their own homes, on their own time.

### **3. Study Design**

We plan to perform an unmasked, non-inferiority randomized controlled trial to determine if the quality of life is improved with the use of TENS compared to PTNS for urgency urinary incontinence and overactive bladder. The target population is patients with OAB and/or urgency urinary incontinence (UUI) who present to the urogynecology clinic either at the University of New Mexico Hospital (UNMH) or Sandoval Regional Medical Center (SRMC). Women will be informed of the arm of the study to which they are randomized, as the intervention is unable to be masked. Masking is not possible with this study design due to the nature of the interventions. All women will give written consent prior to enrollment.

### **4. Inclusion and Exclusion Criteria**

- 4.1. We will recruit women with OAB and/or UUI who present to the University of New Mexico Urogynecology practice at UNM Eubank Clinic (UNM) or Sandoval Regional Medical Center (SRMC) with OAB, urgency urinary incontinence (UUI) without other types of incontinence, or mixed urinary incontinence with urge predominant-symptoms who have failed a trial of at least one medication. To confirm diagnosis and eligibility, we will conduct

PROTOCOL TITLE: INTENSE: INvestigation of TENS Efficacy versus Posterior Tibial Nerve Stimulation for overactive bladder

a standard intake history and physical, complete with cough stress test, POP-Q pelvic examination, urinalysis and urine culture. If the potential participant predominantly complains of OAB or UUI, she will be introduced to the study and provided with written information that may help her decide if participation in the study is right for her. All potential participants will be counseled about possible treatment options for OAB and UUI including non-surgical and surgical techniques. If a woman is withdrawn from the study either by her desire or that of the research staff, or does not desire to participate, she will be offered the same treatment options. Her follow up appointments will be the same regardless of participation in the study. The rationale for targeting this population is that these are women who would routinely be offered third line treatments for OAB or UUI.

4.2. Patients will be enrolled if they meet the inclusion and do not meet the exclusion criteria.

4.2.1. Inclusion Criteria

- Female Subjects  $\geq 18$  years of age
- OAB, UUI or Mixed Urinary Incontinence with urgency predominant symptoms and more bother from UUI than stress urinary incontinence
- Failed trial of conservative therapy (including bladder training, fluid modification, diet modification, caffeine restriction, or pelvic floor training)
- Failed trial of at least one pharmacologic treatment (anticholinergics,  $\beta 3$ -adrenoceptor agonist) either due to inability to take the medication, adverse reaction to medication, or no improvement on medication
- Willing to complete study questionnaires
- Willing to adhere to 12 office visits for PTNS over 3 months if randomized to that arm
- No contraindication to undergoing PTNS or TENS therapy

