## 8. Research Setting

- 8.1. The study will be performed at the University of New Mexico (UNM) Eubank Women's Primary Care Clinic and Sandoval Regional Medical Center (SRMC) Urogynecology clinics. These Urogynecology clinics are dedicated to care of women with pelvic floor disorders such OAB, the target population for this study.
- 8.2. Potential subjects will be recruited in the UNM Eubank and SRMC clinics when they present for care for OAB/UII, either in person or virtually via telephone or Zoom care visits. All patients will have a history and physical taken to determine their study eligibility. Recruitment will take place either in private exam rooms at these clinics or over HIPAA-compliant telephone or Zoom conversation. After recruitment, they will undergo the informed consent via the same means as recruitment and complete initial questionnaires in clinic or will be sent a copy (digital or mail) to complete if enrolled virtually. Patients in the TENS group will be given their TENS device in clinic and research staff will assist in educating participants on proper placement and use of the device, as well as provide a standardized treatment protocol they will complete at home. The patients randomized to PTNS will have their sessions at the UNM Eubank Women's Primary Care Clinic.
- 8.3. There are no other laboratory tests in this trial beyond what would routinely be collected in the work up of OAB.
- 8.4. There will not be involvement of any community advisory board.
- 8.5. There will not be any research conducted outside of the UNM HSC and its affiliates.

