## 12. Procedures

This non-blinded, non-inferiority randomized controlled trial will be conducted at the UNM Eubank Clinic and SRMC Urogynecology clinic. Each site will recruit participants and we will plan to obtain up to 130 women between the two sites. Collaborating investigators will be members of the Urogynecology Division at UNM HSC.

The primary aim of our study is to determine if symptoms and quality of life related to overactive bladder are improved similarly with TENS use versus PTNS in women with OAB/UUI. The target population will be patients with OAB or UUI who are seeking care after failing first- and second-line therapies. According to the American Urologic Association, first line therapy includes conservative treatments like bladder training, bladder-control strategies, pelvic floor muscle training or fluid management. Second-line treatment includes pharmacologic management with anti-muscarinic and  $\beta$ 3-adrenoceptor agonist medications. Subjects must have failed a trial of at least one medication (use with no improvement in symptoms for at least 8 weeks, or a contraindication to taking medication such as narrow angle glaucoma, use of other medications that would interact with anticholinergics, uncontrolled hypertension, allergic reaction or adverse side effect to an anticholinergic medication). The subject may have stress urinary incontinence, but urinary urgency or urgency urinary incontinence must be a bothersome complaint or symptom. The current standard-of-care recommendation for those with refractory OAB or UUI who have failed first- and second-line therapies is to offer patients third-line treatment with PTNS, sacral neuromodulation, or intradetrusor injection of onabotulinumtoxinA. For patients who present for treatment of refractory OAB or UUI, we will take a thorough history and physical and counsel the patient on all of her options including medical and surgical interventions.

If the patient is interested in non-surgical management with PTNS and fulfills study inclusion criteria, we will then offer her the choice of volunteering for the study. All women will give written and/or electronic consent prior to their enrollment at this time and fill out baseline questionnaires in the clinic. Research staff and clinicians will obtain consent and administer study. After enrollment, participants will fill out a baseline OAB-q and will be

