participation in the study or outcome measurement will not be extended further than 13 weeks after randomization. However, they will not be withdrawn from the study for missing sessions, and will be followed for outcomes and adverse events despite missing sessions of PTNS. Women that miss more than one session of PTNS or miss one session and do not make it up at the end will be considered “not fully compliant” with PTNS treatment, and will be analyzed in the “intention-to-treat” analysis in the PTNS arm but not in the “per protocol” analysis in the PTNS arm.

Prior to their week 6 session, women will be asked to complete a 3-day voiding diary in the three days before their scheduled PTNS treatment and bring it to clinic. At their week 6 session, women will complete the UDI and PSQ questionnaires via REDCAP on an iPad in clinic. The same will be conducted for their week 12 session. Patient compliance of attending PTNS sessions will be recorded.

**12.1.2. TENS:** Women randomized to the TENS groups will begin therapy after their baseline evaluation is complete. They will be asked to purchase a TENS 7000 device (estimated cost \$30) and will administer self-treatment at home, daily for 20 minutes, for 12 weeks total. Current practice in the Urogynecology clinic is to offer TENS therapy to women as an alternative to in-person maintenance therapy for after completing PTNS 12 sessions. TENS 7000 device is off label for its use in the treatment of OAB. If funding is secured, women in both PTNS and TENS group will be reimbursed with a merchandise card. Participants will be asked to bring their device to clinic to ensure the correct device is used, standardize settings and provide the following patient education:

- Proper TENS device set up and pre-set standardized settings, detailed below
- Proper electrode pad placement that will be demonstrated. Electrodes will be traced with a skin marker during this clinic visit and pictures will be provided to ensure correct placement at home. If the patient has a camera, they can photograph electrode placement while in clinic.
- Determine intensity level
- Patients will be notified that they can go about their regular daily activities with the TENS device in place, so that treatment does not interfere with normal work or household duties. However, they will be instructed to not use the device while exercising due to sweat causing reduced adhesive function of electrodes and possible displacement.

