**22. Economic Burden to Subjects**

The cost of the TENS 7000 device and associated materials will be the responsibility of the subject if randomized to the TENS group. If funds become available, we will plan to compensate participants in both the PTNS and TENS arms with a \$50 merchandise card. Participants will not be billed for any other study materials.

Participants have already chosen to undergo third line, non-surgical treatment of their OAB/UII and will receive prior authorization from their third-party payers if randomized to PTNS or will have worked out financial assistance if needed. These costs will be billed to their insurance provided and costs may range from copay only to full cost of treatment.

Research Procedures	Number of Samples/Procedures	Responsible Party	
		Study	3 rd Party Payer or Participant
TENS Device	1		
_____	_____		
Standard of Care Procedures	Number of Samples/Procedures	Responsible Party	
		Study	3 rd Party Payer or Participant
PTNS Treatment	12		
Clinic visit	1-2		
Transportation to PTNS treatment	0-12		
Transportation to Clinic Visits	1-2		
Phone Visit – remote	2		
_____	_____		
_____	_____		
_____	_____		

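### Willingness is checked for PTNS only and TENS women are asked to buy their device after allocation, so refusals at allocation could leave a selected TENS arm

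*Combined protocol and SAP*

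**What the plan says.** **Eligibility.** Section 4.2.1 asks that a woman be "Willing to adhere to 12 office visits for PTNS over 3 months if randomized to that arm". The only criterion there that names TENS is "No contraindication to undergoing PTNS or TENS therapy". Nothing asks whether she would treat herself at home each day for 12 weeks, or obtain the device.

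**Invitation.** Section 12 describes who is approached: "If the patient is interested in non-surgical management with PTNS and fulfills study inclusion criteria".

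**Timing and supply.** Randomisation follows consent and baseline data (Section 12). Of women then allocated to TENS, Section 12.1.2 says "They will be asked to purchase a TENS 7000 device", at an estimated 30 dollars, and bring it to clinic to be checked and set. Section 15 refers to the device as one the participant purchased. Section 22 says the cost "will be the responsibility of the subject if randomized to the TENS group". Section 8.2 says instead: "Patients in the TENS group will be given their TENS device in clinic". Section 23 makes any merchandise card conditional on funding and payable only at 6 and 12 weeks.

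**Leaving the study.** Sections 4.1 and 20 offer a withdrawn woman the same treatment options. Section 13.2 analyses women as randomised, with an exception for those who asked to be withdrawn or whom investigators withdrew for safety or validity reasons.

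**The concern.** The plan recognises that acceptance of the allocated treatment matters, yet tests it for one arm. A woman who came for PTNS and does not want home TENS, or will not buy a unit, can pass every criterion and is already randomised when this becomes clear. The trial is unmasked, so she knows at once that she did not get the treatment she asked about.

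What follows depends on what she does:

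- If she asks to be withdrawn, Section 13.2 takes her out of the primary analysis. A PTNS arm screened for acceptance is then compared with a TENS arm that has selected itself for acceptance after randomisation.
- If she stays in follow-up untreated, TENS looks worse.
- If she stays in follow-up but has PTNS outside the study, the arms converge, which favours a non-inferiority claim.

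The contradiction about supply adds to this, because a woman who expects to be given a device may learn only after allocation that she must buy it.

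**Working it through.** **1. What is checked for each arm**

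| | PTNS | TENS |
|---|---|---|
| Willingness criterion (4.2.1) | Yes, 12 visits | None |
| No contraindication (4.2.1) | Yes | Yes |
| Interest named in the invitation (12) | Yes | No |
| Payment | Prior authorisation or financial assistance described (22) | Participant buys (12.1.2, 15, 22) or is given the device (8.2) |

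**2. The planned allowance for loss.** Section 5.3 needs 40 per group (80 in total) and allows 30% dropout: 80 / 0.70 = 114.3, which agrees with the stated 114. The 30% is not split by arm.

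- At 114 randomised 1:1: 57 per arm; 57 − 40 = 17 losses allowed (17/57 = 29.8%).
- At 130, if all are randomised: 65 per arm; 65 − 40 = 25 losses allowed (25/65 = 38.5%).

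**3. Sensitivity to unequal loss (illustration only).** The documents give no SD, no sidedness for alpha and no refusal rate. Solving 40 per group backwards for a 10-point margin, zero true difference and 80% power:

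SD = 10 / [√(2/40) × (z₁₋α + z₀.₈₀)]

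- One-sided 0.05: 10 / [0.2236 × (1.645 + 0.842)] = 17.99
- One-sided 0.025: 10 / [0.2236 × (1.960 + 0.842)] = 15.96

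Power = Φ(10/SE − z₁₋α), with SE = SD × √(1/n_PTNS + 1/n_TENS). PTNS loss is held at 30% and TENS loss is assumed. Ranges span the two alpha readings.

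| TENS loss (assumed) | 57 per arm | 65 per arm |
|---|---|---|
| 30% | 0.80 | 0.84–0.85 |
| 40% | 0.77 | 0.82 |
| 50% | 0.72–0.73 | 0.78 |

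Worked case, 57 per arm, 40% TENS loss, one-sided 0.05: n = 39.9 and 34.2; SE = 17.99 × √(1/39.9 + 1/34.2) = 4.19; 10/4.19 − 1.645 = 0.74; power 0.77.

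Recruiting to 130 therefore offsets a moderate imbalance in numbers. It does nothing about who remains.

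**4. Non-starters kept in follow-up (illustration only).** Suppose a share of the TENS arm never starts and improves 10 points less (both assumed), with 40 analysed per arm. A 10% share builds in a difference of 0.10 × 10 = 1 point and power is 0.71–0.72. A 20% share builds in 2 points and power is 0.61–0.64.

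**5. Recruitment.** Section 6.1 gives 10 to 20 eligible women a month and 25% enrolment: 2.5 to 5 a month, or 60 to 120 in 24 months, against a target of up to 130.

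**The case against.** Consent does part of this screening. Women are randomised only after signing, with written information and time to decide, and agreeing to a two-arm trial implies accepting either arm. That has weight, but the same is true of PTNS, for which the plan still wrote a separate criterion. A reader might infer that the purchase is not disclosed beforehand. The consent form is not among the documents, so that cannot be said.

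A reader might also infer that refusal and dropout will concentrate in TENS. The documents do not support that. PTNS can cost from a copay to the full price (Section 22) and may need up to 12 journeys. Section 2 calls the weekly visits a significant barrier. Prior authorisation is described for women randomised to PTNS, so non-start is possible there too. Section 1.2.3 expects better compliance with TENS, and Sections 5.3 and 13.4 single out PTNS when expecting a smaller per-protocol sample. This stands: net attrition could run either way. It does not remove the narrower point, because later PTNS losses would not cancel selective refusal of TENS at allocation.

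Other parts of the protocol describe the population as women wanting non-surgical management generally (Sections 1.1, 18 and 19), so the PTNS wording in Section 12 may be loose drafting. Section 8.2 is the outlier on supply. TENS women who miss sessions are followed and kept in intention-to-treat (Section 12.1.2), and untreated women in that set push against a non-inferiority claim. Section 15 also stops the study intervention and PTNS device on withdrawal, so access to PTNS afterwards rests on the general statements in Sections 4.1 and 20.

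**Conclusion.** The point holds as a risk created by the wording. It is certain that willingness is tested for one arm, that the invitation in Section 12 names PTNS alone, that purchase is requested after allocation, and that Section 8.2 contradicts Sections 12.1.2, 15 and 22. It is an inference that refusal or non-start at allocation may fall more on TENS and, through the exception in Section 13.2, leave a selected TENS arm.

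The size is unknown. The allowance is 17 losses per arm at 114 and 25 at 130. A reader might assume 10% to 20% TENS non-start and conclude that 6 to 11 of the 17 are used up (57 × 0.10 = 5.7; 57 × 0.20 = 11.4). No such rate is in the documents, nothing says the 30% allowance excludes non-starters, and women who do not start but are followed are not lost to intention-to-treat. The power figures above rest on a back-solved SD and assumed loss, and show sensitivity only. The direction of any bias is also open, since it depends on whether refusers withdraw, stay untreated or have PTNS outside the study. The change is worth making because it is cheap and acts before randomisation.

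**What to change.** 1. Add to Section 4.2.1 a criterion matching the PTNS one: willing to obtain the study TENS device and follow the TENS schedule if randomised to that arm, confirmed before randomisation.
2. Reword the invitation in Section 12 to cover women interested in tibial nerve stimulation by either route.
3. Reconcile Sections 8.2, 12.1.2, 15 and 22 so that one statement says who supplies and pays for the device, and make sure the consent form agrees.

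These are changes to wording. They reduce the number of women who reach the withdrawal exception in Section 13.2 but do not alter that exception. The cost is that women who would accept only PTNS are not enrolled, and, if the participant still pays, some selection on willingness to buy. Both would modestly slow recruitment that is already tight on Section 6.1's figures.
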